Because of the parameters of the study, a chart review and subject interview will be conducted during the screening visit. "Yes" answers to any of the following will result in inability to participate in the study.

- Previous or current use in the last 1 year of finasteride, minoxidil topical or oral, or spironolactone
- A diagnosis of non-androgenic alopecia (i.e.: another diagnosis for the alopecia)
- Abnormal Baseline ferritin, TSH, platelet count, and a negative urine pregnancy test in any pre-menopausal female in past 12 months.
- Active skin disease (Psoriasis or severe seborrheic dermatitis) of the scalp
- Active scalp infection
- Severe active blood infection
- Cuts or abrasions on the scalp
- History of surgical hair restoration
- Current or recent malignancy
- History of systemic chemotherapy or radiation
- History of thyroid dysfunction
- History of autoimmune disorder (specifically Graves disease, hashimoto thyroiditis, or systemic lupus erythematosus)
- Tendency to develop keloids
- Continued medically necessary daily use of Nonsteroidal anti-inflammatory or Vitamin E
- Platelet dysfunction syndrome
- Thrombocytopenia less than 150,000
- Diagnosis of hypofibrinogenemia
- Anticipated pregnancy or trying to become pregnant in the next 2 years
- Current or active Tobacco use

Informed Consent:

Prior to entering the study, the investigator or designated assistant will explain to each subject the nature of the study, its purpose, procedures, expected duration, alternative therapy available, and the benefits and risks involved in study participation. Subjects will be given the consent document, the opportunity to ask questions, and will be informed of their right to withdraw from the study at any time without prejudice. After this explanation and before any study-specific procedures have been performed, the subject will voluntarily sign and date and informed consent form, including photographic consent form. Prior to participation in the study, the subject will receive a copy of the signed and dated written informed consent form.

Platelet Rich Plasma (PRP) And Saline Injection Guidelines:

3-6ml of PRP will be injected into randomly assigned subjects. The same procedure will be carried out for administration of the normal saline. Both procedures are detailed above.

Safety Evaluations:

Adverse Reactions

At each visit, the subjects will be assessed for any of the following possible AEs:

- -injection site pain
- -ecchymoses

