- persistent or significant disability/incapacity
- congenital anomaly/birth defect

An event may be considered serious when, based upon appropriate medical judgment; it jeopardizes the patient or subject and may require medical or surgical intervention to prevent one of the outcomes listed above.

A life-threatening adverse event is any AE or adverse drug reaction that at any dose places the patient or subject, in the view of the investigator, at immediate risk of death from the reaction as it occurred. It does not include a reaction or event that, had it occurred in a more severe form, might have caused death.

Materials And Supplies:

Study Device

Eclipse will manufacture and provide the PRP collection kits for use in the study. The PRP will then be injected into the scalps of patients for the treatment arm of the study. Normal saline will be used for the placebo arm of the study.

Syringes and 25 G needles will be used.

Gauze, alcohol swabs will be used to prepare the injection sites.

Institutional Review Board:

Prior to beginning this study, approval must be obtained from the Institutional Review Board at the Mount Sinai Medical Center.

Data Analysis:

Individual efficacy variables, the sum of those variables, and safety parameters will be analyzed.

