**The Effect of Platelet Rich Plasma on Non-scarring Alopecia**

**PI: [name]**

**NCT03689452**

**Document Date: 9/21-2018**

**The Effect of Platelet Rich Plasma on Non-scarring Alopecia:  
A Randomized, Controlled Clinical Trial**

**PI:** [name]

**Date:** 9/21/18

*Statistical analyses*

Statistical analyses will be performed using SAS version 9.4 (SAS Institute Inc., North Carolina, United States). Difference scores from baseline to week 8 and from baseline to week 24 will be calculated for both hair density and caliber. The PRP and saline groups will be compared on these difference scores using independent samples t-tests. The difference scores will also be dichotomized based on whether the change over time was positive or negative. The PRP and saline groups will be compared on these dichotomized scores using chi-square tests. All given p-values will be two tailed and a p-value of less than 0.05 will be regarded as indicating statistical significance.

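### Each change score is tested twice, by t-test and by chi-square on its sign, both at p < 0.05 with neither ranked, and a change of exactly zero has no category

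*SAP*

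**What the plan says.** The SAP (Statistical analyses) defines four change scores: "Difference scores from baseline to week 8 and from baseline to week 24 will be calculated for both hair density and caliber". It then sets two tests on each of them. The first is continuous: "The PRP and saline groups will be compared on these difference scores using independent samples t-tests". The second reduces the same scores to their sign: "The difference scores will also be dichotomized based on whether the change over time was positive or negative", followed by "The PRP and saline groups will be compared on these dichotomized scores using chi-square tests".

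One sentence governs all of the resulting p-values: "All given p-values will be two tailed and a p-value of less than 0.05 will be regarded as indicating statistical significance". That makes four t-tests and four chi-square tests. None is called primary or supportive, no clinical reason is given for cutting at zero, and no rule covers a change of exactly zero.

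The protocol does not settle the order. Its Primary endpoint section names photography and trichoscopy without an analysis, and its Data Analysis section says only "Individual efficacy variables, the sum of those variables, and safety parameters will be analyzed".

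**The concern.** Three things follow from the text.

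- **The size of the change is lost.** A trivial gain counts the same as a large one. With symmetric measurement noise, about half of subjects with no true change are counted as positive.
- **Zero has no place.** A change of exactly zero is neither positive nor negative. Unless a rule is fixed now, someone will choose one after seeing the data.
- **Two unranked tests run on the same data.** If one is significant and the other is not, the SAP does not say which decides. A significance claim could then rest on the coarser test alone.

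At stake is whether the trial's conclusion on density or caliber at a given visit is fixed in advance.

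**Working it through.** **Inputs.** From the SAP: two-sided 0.05 per test, t-test on change, chi-square on the sign of change. Neither document states a sample size, SD, effect size, saline change or allocation ratio, so there is no planned figure to reproduce. Assumed: normal changes with equal SD (set to 1), 1:1 allocation, effect d in SD units, saline mean change m. Two designs give about 80% t-test power: 26 per arm at d = 0.8, and 64 per arm at d = 0.5.

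**Step 1: t-test power.** Noncentral t with 2n − 2 degrees of freedom and noncentrality d × √(n/2).
- n = 26, d = 0.8: 0.8 × √13 = 2.88, power 80.7%.
- n = 64, d = 0.5: 0.5 × √32 = 2.83, power 80.1%.

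**Step 2: chi-square power.** P(change > 0) is Φ(m) on saline and Φ(m + d) on PRP. Power is the exact sum of the two binomial probabilities over all tables where the uncorrected Pearson statistic exceeds 3.84.

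| n per arm, d | m | P(positive) saline / PRP | Chi-square power | Points below t-test |
|---|---|---|---|---|
| 26, 0.8 | 0 | 0.50 / 0.79 | 61.4% | 19.4 |
| 26, 0.8 | +0.5 | 0.69 / 0.90 | 51.1% | 29.7 |
| 26, 0.8 | +1 | 0.84 / 0.96 | 32.7% | 48.1 |
| 64, 0.5 | 0 | 0.50 / 0.69 | 61.4% | 18.8 |
| 64, 0.5 | +0.5 | 0.69 / 0.84 | 52.3% | 27.9 |
| 64, 0.5 | +1 | 0.84 / 0.93 | 37.8% | 42.4 |

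The differences were taken before rounding. The gap widens with m because most subjects in both arms then fall on the same side of zero. The SAP does not say whether a continuity correction applies. With one, the gap grows: at n = 50, d = 0.5, m = 0, the t-test has 69.7%, the uncorrected chi-square 51.0% and the corrected one 42.8%.

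**Step 3: outside those assumptions (normal changes, exact).**
- n = 10, d = 0.5, m = 0: 18.5% against 12.0%, a gap of 6.5 points.
- n = 50, d = 1.0, m = 0: a gap of 3.4 points.
- n = 64, d = 0.5, m = +1.5: a gap of 59.4 points. At n = 26, d = 0.8, m = +1.5 it is 73.7.

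**Step 4: heavy-tailed changes (simulated).** With Laplace changes, n = 64, d = 0.5, m = 0, the t-test has 80% and the chi-square 86%. With t on 3 degrees of freedom, same design, the figures are about 84% and 91%. With Laplace changes and m = +0.5, the chi-square is again the weaker test.

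**Step 5: how often the tests disagree (normal changes, 40,000 simulated trials per case; m = 0, +0.5, +1).**
- n = 26, d = 0.8: t-test significant and chi-square not in 22%, 32% and 50% of trials. The reverse occurs in about 2%.
- n = 64, d = 0.5: 21%, 30% and 44%. The reverse occurs in about 2%.

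Total disagreement is therefore about 24% to 51%.

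**Step 6: no true effect.** For n from 20 to 64 per arm, at least one of the two tests is significant in about 7 to 8% of trials, and in about 9% in the highest case. This is for one outcome at one visit. Two independent tests would give 1 − 0.95² = 9.75%.

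**The case against.** The strongest reply is that the plan gives up nothing. The t-tests come first, the SAP says the scores will *also* be dichotomised, and nothing makes the chi-square decisive. This stands. A reader might infer that the trial itself loses some 20 to 45 points of power. The documents do not support that: the gap lies between two tests that are both planned, and it matters only if the weaker one is allowed to decide.

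A second reply is that the size of the gap rests on assumed inputs, and that its direction depends on the distribution. This also stands. A reader might conclude that the sign comparison can never add anything to the mean difference. Step 4 shows otherwise for heavy tails without saline drift, and the share of women who gained hair is a readable summary in its own right.

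A third reply is that the ambiguity comes from the missing ranking and not from dichotomising, and that equal standing is inferred from one general sentence on significance. This is partly right, and ranking the tests would resolve the conflict. But that sentence covers every p-value, and nothing in either document places the chi-square below the t-test.

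Finally, measurement precision is not stated, so exact zeros may be rare, particularly for caliber. That limits how much the zero gap matters but does not close it.

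**Conclusion.** The concern holds in limited form. As written, each of the four change scores has two unranked routes to significance, one of which ignores the size of the change and leaves zero undefined. This raises the chance of a false positive for one outcome at one visit from 5% to about 7 to 8%.

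Under normal changes, 1:1 allocation, d of 0.5 or 0.8 SD, about 80% t-test power and a saline mean change of 0 to +1 SD, the chi-square has about 19 to 48 points less power, and the two tests give different answers in about a quarter to a half of trials. These are conditional figures and not properties of this trial. Elsewhere the gap runs from a few points to 60 or more, and it can reverse with heavy tails. The t-test's own power is unaffected throughout.

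**What to change.** Amend the SAP before the data are analysed:

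1. Name the between-group difference in continuous change, with its 95% CI, as the inferential analysis for density and caliber.
2. Report the percentage with positive change in each arm as descriptive or supportive, with a CI for the difference in proportions and no stand-alone significance claim.
3. Class a change of exactly zero as not improved.

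This changes wording only, with no effect on visits, measurements or data collected. The cost is that four p-values can no longer carry a significance claim, including in cases where heavy-tailed changes would have favoured the sign comparison.

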- 2. Study visit 2: Injection #1, week 0: FULL PHOTO EVALUATION AND SURVEY #1
- 3. Study visit 3: Injection #2, week 4
- 4. Study visit 4: Injection #3, week 8: FULL PHOTO EVALUATION
- 5. Study visit 5: Injection #4, week 24: FULL PHOTO EVALUATION AND SURVEY #2
- 6. Study visit 6: final assessment visit only, no injections, week 40: FULL PHOTO EVALUATION AND SURVEY #3

At each injection visit (weeks 0,4,8,24) the participant will first speak to the doctor and discuss any adverse reactions. Photographs will be taken as mentioned above. On certain visits, as listed, patient surveys will be given to subjects to assess PRP, any improvements in the alopecia, pain or other adverse effects. The data from these surveys will be used in the final stages of the research to look at patient aggregated data. After this, the injection protocol will be followed as detailed above and the patient will be scheduled for their next appointment.

Patients will be contacted within 12-24 months post study to be informed of results of the study. If possible and if published by this time, a copy of the paper outlining the trial will also be provided to patients.

Primary endpoint:

Photographs of the scalp (with standard digital camera) and trichoscopy photographs (with specialized camera called folliscope to visualize hair follicles and measure hair thickness, density, and caliber where the follicle exits the scalp) will be used for primary evaluation endpoint.

Secondary endpoint:

Additionally, surveys as detailed above will provide qualitative participant information regarding improvement with procedure, pain or other adverse effects.

Subject Selection:

Inclusion Criteria

- 1. Must understand and voluntarily sign an informed consent form
- 2. Must be female between the ages of 18 and 65 years at the time of consent
- 3. Must be able to adhere to the study visit schedule and other protocol requirements
- 4. Documented baseline blood work either in chart review or documented by the hair loss clinician- blood work needed includes normal TSH and ferritin as per the laboratory standards, platelet count above 150,000 platelets per microliter and a negative pregnancy test for any premenopausal women—all blood work must be documented as normal within 12 months prior to the start of the study

Exclusion Criteria

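### Eight overlapping tests are each called significant at p<0.05 with no primary variable, visit or test; if any one counts, the false-positive chance is about 11–30% under stated assumptions

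*SAP*

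**What the plan says.** The SAP's statistical analyses paragraph sets up four change scores: "Difference scores from baseline to week 8 and from baseline to week 24 will be calculated for both hair density and caliber". Each is tested twice. First, "The PRP and saline groups will be compared on these difference scores using independent samples t-tests". Then the same scores are cut at zero: "The difference scores will also be dichotomized based on whether the change over time was positive or negative", and "The PRP and saline groups will be compared on these dichotomized scores using chi-square tests". The only decision rule covers every result alike: "All given p-values will be two tailed and a p-value of less than 0.05 will be regarded as indicating statistical significance".

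The protocol adds no ranking.

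- Its Primary endpoint section names scalp photographs and trichoscopy, the latter to "measure hair thickness, density, and caliber where the follicle exits the scalp) will be used for primary evaluation endpoint". Three measurements stand side by side and no visit is attached.
- Its Protocol Schedule lists "Injection #3, week 8: FULL PHOTO EVALUATION" and "Injection #4, week 24: FULL PHOTO EVALUATION AND SURVEY #2", and a further full photographic assessment at week 40. None is marked as the primary visit.
- Its Data Analysis section mentions individual efficacy variables and also a summed score, without saying whether the sum leads, supports or is simply one more comparison.

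**The concern.** A reader of the results cannot tell which comparison decides the trial. With eight p-values each judged at 0.05, the main conclusion can settle after the fact on whichever is smallest, and the chance of a false finding then exceeds the 5% that each test appears to promise. Mixed results have no rule either: density may reach significance when caliber does not, week 8 when week 24 does not, or a t-test when the chi-square on the same score does not. These eight tests are the whole of the SAP's efficacy analysis, so the gap affects the trial's central claim.

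**Working it through.** **Count.** 2 variables × 2 intervals × 2 tests = 8 tests on 4 change scores (SAP). Each is two-sided at 0.05 (SAP). The plan states no overall error rate, so there is no figure of its own to reproduce.

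**Reference points if the tests were independent.** 1 − 0.95^8 = 0.337 for eight tests; 1 − 0.95^4 = 0.185 for four. The eight-test value overstates the matter, because a t-test and its chi-square use the same score and the four scores are probably correlated. Hence a simulation.

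**Assumptions, none of them in the documents.**

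- Normal changes and no true difference between arms.
- 15, 20, 30 or 50 per arm at 1:1, or 20/10, 40/20 or 66/33 at 2:1.
- A change common to both arms of 0 or 0.5 SD.
- Density–caliber/between-visit correlations of 0/0, 0.3/0.6, 0.5/0.7, 0.7/0.8 and 0.9/0.9.
- 20,000 trials per setting, run twice: 7 × 2 × 5 × 2 = 140 setting-runs.

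Each trial counts as a false finding if any test in the set has p<0.05. The SAP does not say whether the chi-square is continuity-corrected, so both forms are shown.

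| Any false significant result among | Either direction (one test: 5%) | In PRP's favour (one test: 2.5%) |
|---|---|---|
| Eight tests, uncorrected chi-square | 0.154–0.300 | 0.079–0.162 |
| Eight tests, corrected chi-square | 0.107–0.244 | 0.055–0.131 |
| Four t-tests only | 0.092–0.192 | 0.047–0.101 |

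**Stronger correlation, eight tests, either direction.**

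| Correlations | Uncorrected | Corrected |
|---|---|---|
| 0.95/0.95 | 0.134–0.164 | 0.095–0.128 |
| 0.97/0.97 | 0.125–0.150 | 0.087–0.117 |
| 0.99/0.99 | 0.104–0.131 | 0.073–0.102 |

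The rate fell below 10% only with continuity correction and both correlations at 0.95 or more. A separate run on a wider grid (10–100 per arm at 1:1, common change up to 1 SD, correlations 0 to 0.95, uncorrected chi-square) gave about 11–32%.

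**Check of the remedy, same null settings.** The Monte Carlo standard error at 0.05 is √(0.05 × 0.95 / 20,000) = 0.0015.

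- Gated sequence, all nulls true: 0.045–0.053.
- Primary effect real and always detected, second variable null: 0.045–0.054.
- First two steps real and detected, Holm over the other SAP visit's two t-tests, both null: 0.034–0.052.
- Holm over four t-tests as the only family: 0.025–0.052.
- For contrast, a Holm family over the other visit's two t-tests run without waiting for the primary: 0.061–0.101.

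**Power cost of four-test Holm.** The smallest p is compared with 0.05/4 = 0.0125 (z = 2.498). A comparison with 80% power at 0.05 then has power Φ(1.960 + 0.842 − 2.498) = Φ(0.304) = 0.619. The noncentral t gives 0.596, 0.602, 0.608 and 0.613 at 15, 20, 30 and 50 per arm.

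**The case against.** The strongest reply is that the SAP never says a single significant result would make the trial positive. A reader might infer that the plan has a 30% false-positive rate, or even the 34% of eight independent tests. The documents do not support that. They contain no any-one-counts rule, sample size, allocation or correlations, and the tests overlap by construction. The rates are conditional on both the reading and the assumptions.

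A reader might also take 11–30% as the risk of a false claim that PRP works. That range counts results in either direction; in PRP's favour it is 5.5–16% against 2.5%, much the same relative inflation but about half the absolute size.

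The SAP introduces the dichotomized comparison as an addition, so the chi-squares may be meant as supportive. That is a fair reading, though the significance rule covers them equally, and the four t-tests alone still give about 9–19%. High correlation helps, but even at 0.95–0.99 the eight-test rate is about 7–16%. Finally, making the t-test decisive is a reasonable choice, not one the documents compel.

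These points limit the precision of the figures. None supplies a primary comparison or an adjustment.

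**Conclusion.** The concern holds. The SAP gives eight overlapping comparisons equal standing at p<0.05, and neither document ranks or adjusts them. That much needs no simulation.

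The size rests on the assumptions listed and on any one result being read as an effect. With correlations up to 0.9/0.9, the either-direction rate is about 15–30% (uncorrected chi-square) or 11–24% (corrected), against 5%. In PRP's favour it is about 8–16% or 5.5–13%, against 2.5%. The documents do not show that the sponsor intends to claim success on any single result; the defect is that the plan leaves this open. Because it concerns the main efficacy conclusion, it must be settled before outcomes are compared by group.

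**What to change.** Before any comparison of outcomes by group:

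1. The sponsor names and justifies one primary variable at one visit, tested by t-test at two-sided 0.05. The choice is the sponsor's, since the documents rank neither variables nor visits. Protocol and SAP state the same choice.
2. The other variable at that visit is tested by t-test at 0.05 only if the first is significant.
3. All other comparisons (other visits, any summed score, the positive/negative split) are reported as estimates with 95% confidence intervals and no significance claim.
4. If t-tests at the remaining SAP visit or visits are to carry a claim, they form one Holm family, opened only after both earlier steps are significant. A Holm family run at full 0.05 beside a separately tested primary must not be used.
5. If variables and visits cannot be ranked, steps 1–4 are replaced by a single Holm procedure over all planned t-tests as the sole confirmatory family. That is four tests as the SAP stands (smallest p against 0.05/4 = 0.0125), or six if week 40 is added for both variables (0.05/6 = 0.0083).

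The cost is SAP wording and a matching protocol statement. An isolated p<0.05 outside the sequence can no longer be claimed as significant. Under four-test Holm, a comparison with 80% power at 0.05 keeps about 60–62% at the first step.
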